Effect of Topical Sulforaphane on Skin Fragility Seen in Skin Aging and With Ultraviolet Exposure

NCT03126539

June 16, 2017

Date: 06/16/2017 Principal Investigator: [name], MD Application Number: IRB00105668

Johns Hopkins Medicine - eForm A

Effect of Topical Sulforaphane on Skin Fragility Seen in Skin Aging and With Ultraviolet Exposure

1. Abstract

The cross sectional study investigating whether topical application of sulforaphane (broccoli sprout extract) results in the induction of both keratin 16 and keratin 17 in the basal layer of the epidermis is currently IRB approved (IRB00061421).

The primary purpose of our study is to compare the expression of keratins before and after application of sulforaphane (SF) and determine whether these findings alter skin fragility seen in both intrinsic and extrinsic skin aging as well as in ultraviolet (UV) light exposure.

This investigation will be done in collaboration with researchers from the Department of Biochemistry and Molecular Biology and Bloomberg School of Public Health at Johns Hopkins University. The study population recruited by Johns Hopkins Department of Dermatology will include up to 50 individuals over the age of 18 with healthy skin. Each study participant will have four on-site study visits and will be asked to contribute photographs, undergo non invasive elasticity measurements, use topical sulforaphane for 7 days and contribute up to four biopsy specimens for laboratory study. We will also evaluate any differences in keratins' expression in skin exposed to acute UV light, separately and after pretreatment with sulforaphane.

2. Objectives

- The primary objective of this study is to compare the induction of both keratin 16 and keratin 17 in the basal layer of the epidermis in both photoprotected and photodamaged skin treated with sulforaphane to determine whether SF can improve skin fragility seen in these conditions. This would be visualized by established indirect immunofluorescence assays on skin tissue sections prepared from biopsy material, and would be confirmed and quantified by PCR-based analyses of RNA samples.
- The secondary objective is to investigate distinct keratin expression changes in human skin after acute UV light exposure, separately and in combination with application of topical sulforaphane.

3. Background

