Isothiocyanate sulforaphane (SF), derived from broccoli sprouts, has been known to induce an antioxidant response through the Keap1-Nrf2-antioxidant response element pathway.¹ With its chemoprotective effects as the rationale, it has previously been studied for tolerance and safety in humans and has been shown to have virtually no adverse effects.²⁻⁴ This includes a study in which sulforaphane-containing broccoli sprout extracts was formulated in acetone and topically applied to the skin. ² Additionally, a recent study has shown that oral sulforaphane was safely tolerated in doses of 50-150 µmol daily in children with autism. ⁵

SF selectively induces K17 and K16 in skin keratinocytes. Local activation of two distinct signaling pathways, hedgehog and Keap1/Nrf2/ARE, rescued skin blistering in an epidermolysis

bullosa simplex mouse model, correlating SF with the reprogramming of keratin synthesis in epidermis and improving skin fragility.⁶

Sulforaphane might also help in maintaining the collagen levels during photoaging via the inhibition of the AP-1 activation and of the MMP expression. A previous study reported that SF had preventive effects on UV-induced MMP expression, inhibiting the MMP-1 and MMP-3 expression by blocking the NF-jB pathway.⁷

Aging of human skin may result from both the passage of time (intrinsic aging) and via exposure to external factors (extrinsic aging) such as sunlight (photoaging).⁸ One hallmark feature of skin aging, regardless of type, is skin thinning or fragility. This is partially due to the breakdown in dermal collagen. An increase in MMP-1 after UV exposure is observed in skin. MMP-1 is an interstitial collagenase able to hydrolyze type I collagen, the major component of the dermis, and plays a crucial role in the disorganization and progressive degeneration of dermal extracellular matrix.⁸

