Cutometer: Cutometer readings will be taken from photoprotected and photoexposed areas, before and after sulforaphane and after jojoba oil only application on Group A and from normal skin, Test Area #1 and #2 after UV irradiation on Group B. The cutometer, frequently used in cosmetic dermatology research, applies precise suction to a small area of the skin (6mm diameter). Skin is drawn into the aperture of the probe via negative/vacuum pressure and after a defined time, released again. The resistance of the skin to the negative pressure (firmness) and its ability to return into its original position (elasticity) are displayed as curves (penetration depth in mm/time) in real time during the measurement. This measurement principle provides information about the elastic and mechanical properties of skin surface and enables the study team to objectively quantify skin aging. The procedure is non-invasive and does not cause any discomfort.

Ballistometer: Ballistometer readings will be taken from photoprotected and photoexposed areas, before and after sulforaphane or jojoba oil only application in Group A and from normal skin, Test Area #1 and #2 after UV irradiation on Group B. The ballistometer allows us to measure skin firmness and elasticity by dropping a small probe onto the skin. After the collision of the probe with the skin's surface, we measure the rebound height of the probe. The number of rebounds and amplitude of the rebounds provide information about the rate of energy dampening and bounce profile of the skin's surface. Again, this is a non-invasive procedure and does not cause any discomfort. UV light irradiation: We will use a Lumera UVB light phototherapy device which allows for targeted delivery of controlled doses of UVB radiation (emission spectrum 290-320 nm).

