It is possible that there will be skin irritation of the skin. Risks include irritant dermatitis and/or contact dermatitis, itching sensations from the sulforaphane. Risk events, problems, and deviations will be immediately reported by the PI to the IRB.

Risks include potential bleeding and a slight risk of infection from the punch biopsies. As with any cut in the skin, a scar will develop, although its appearance will likely fade over time. We will screen carefully for keloids in our exclusion criteria, but in rare individuals with no prior keloid history, keloids or excessive scarring may develop at the biopsy site. As with any biopsy, there is a risk of pain or discomfort from the procedure.

There are no anticipated risks or discomforts associated with gross mechanical measurements of elasticity.

There is a risk of sunburn from the UV treatment, although the risk is minimal given the small area affected and limited numbers of treatments. There is a risk of ultraviolet injury to the eyes. Both the operator and subjects will wear UV blocking protective eyewear provided by the device manufacturer. The provided eyewear meets the ANSI Z87.1-2003 standard and blocks 99.9% of UV in wavelengths 180-380 nm and has wrap-around side shields. In addition, the treatment area is the buttock, so even inadvertent eye exposure is highly unlikely.

In terms of confidentiality, there are minimal risks as all study participant information will be de-identified. Since this is an exploratory study, no confidential or protected information would be taken outside of the standard. There is a slight financial risk to the participants in the rare event that the above complications occur requiring additional medical care.

9. Benefits

There will be no direct benefit to the participant as a result of this study. Instead, the potential benefit will be to society at large. We hope to better understand the differences on keratins' expression on phototexposed and photoprotected skin, after acute UV light exposure and also if sulforaphane can play a role on this expression and on skin elasticity.

10. Payment and Remuneration

Study participants who undergo all study procedures, including correct application of sulforaphane, non-invasive measurements, UV light irradiation (if in Group B) and biopsies (up to 5 for Group A and up to 3 for Group B) will receive a total of \$100 at completion of the study.

11. Costs

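### The primary objective infers improved skin fragility from keratin induction, but fragility is never defined as an outcome and the skin-mechanics readings belong to no objective or analysis

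*Combined protocol and SAP*

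**What the plan says.** The Abstract (Section 1) gives the purpose as comparing keratin expression before and after sulforaphane and then to "determine whether these findings alter skin fragility seen in both intrinsic and extrinsic skin aging", as well as with UV exposure. The primary objective (Section 2) compares K16/K17 induction in the two skin types "to determine whether SF can improve skin fragility seen in these conditions". It then gives the means: "This would be visualized by established indirect immunofluorescence assays on skin tissue sections prepared from biopsy material", with a result that "would be confirmed and quantified by PCR-based analyses of RNA samples". The secondary objective concerns keratin expression after acute UV, alone and with sulforaphane. Neither objective mentions elasticity.

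Fragility is discussed in the Background (Section 3) but not defined as something to be measured: "One hallmark feature of skin aging, regardless of type, is skin thinning or fragility". The keratin link comes from a mouse model of epidermolysis bullosa simplex, described as "correlating SF with the reprogramming of keratin synthesis in epidermis and improving skin fragility".

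Section 4a also plans cutometer and ballistometer readings. The cutometer principle "provides information about the elastic and mechanical properties of skin surface" and is said to quantify skin aging. Section 9 (Benefits) hopes to learn "if sulforaphane can play a role on this expression and on skin elasticity". Section 7 (Study Statistics) lists only the biopsy assays.

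**The concern.** The objective passes from a molecular response to a functional benefit in one sentence, with no functional outcome in between. A rise in K16/K17 shows that the skin responded to the extract. Whether that skin is less fragile is a separate question, and the Background itself concedes that the role of keratins in the fragility of aging skin has been little studied.

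At stake is the primary conclusion. If fragility has no definition and no assigned measurement, the reader of the results cannot tell what finding would count for or against the claim. The device readings could be drawn in afterwards if they agree and left out if they do not, because no parameter, contrast or test is fixed in advance.

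**Working it through.** No power, error rate, effect size or standard deviation is given, and the point does not depend on them. The check is an inventory of what is measured, set against what is to be concluded, followed by a check of which contrasts the design allows.

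**1. Measurements and their links**

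| Measurement | Where planned | In an objective? | In Section 7? | Called fragility? |
|---|---|---|---|---|
| K16, K17 (immunofluorescence, PCR) | 2; 4a Laboratory studies | Primary; keratins generally in secondary | Yes (assays only) | No |
| K1, K5, K10, K14, Nrf2 | 4a Laboratory studies | Not by name | Yes (assays only) | No |
| Cutometer | 4a; 6 | No | No | No |
| Ballistometer | 4a; 6 | No | No | No |
| Photographs, clinical assessment | 4a | No | No | No |

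That is 2 + 5 = 7 laboratory markers and two devices, with no outcome defined as fragility. The laboratory list is open-ended, but it names no thickness, blister or tear measure.

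**2. Support for the inference.** The Background attributes the thinning or fragility of aging skin partly to loss of dermal collagen, yet no collagen or MMP marker is named among the seven. The keratin-to-fragility step rests on the mouse blistering model. Section 6 reports that another vehicle, Dermabase, induced K16/K17 in hairless mice with no sulforaphane, and that it was rejected for that reason. Induction was therefore treated there as a vehicle effect, with no suggestion that it showed a functional benefit.

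**3. Which elasticity contrasts exist.**
- Group A has two photoexposed forearm areas and one photoprotected inner-arm area. The supply is 7000 nmol at 500 nmol per site per night for 7 nights: 7000 / (500 × 7) = 2 sulforaphane sites. The third site, on photoexposed skin, receives jojoba oil alone. A sulforaphane-minus-vehicle contrast therefore exists on the forearm and not on the inner arm.
- Group B has Test Area #1 (sulforaphane) and Test Area #2 (vehicle), both irradiated and both read after UV. The contrast exists.
- The cutometer paragraph lists Group A readings before and after sulforaphane but only after vehicle, so no vehicle-site cutometer baseline is stated. The forearm contrast must be a comparison after treatment. The ballistometer paragraph can be read as including a vehicle baseline.
- In Group A, up to two punch biopsies are taken at Visit 1 and their sutures stay until day 10-14, while Visit 2 is at up to day 7. The Visit 2 readings may thus be taken near a sutured wound at some sites and not at others.

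**The case against.** The strongest reply is that the documents place the device readings close to fragility. Fragility is called a hallmark of skin aging, and the cutometer is said to quantify skin aging. The Abstract can be read as two steps, keratins first and fragility second, with elasticity measurements listed alongside. Sections 3 and 9 state narrower aims, Section 8 calls the study exploratory, and Section 6 says it is not a clinical trial.

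Much of this stands. A reader might infer that nothing bearing on fragility is measured. That goes too far, because firmness and elasticity are mechanical data and could be offered as an indirect measure. A reader might also infer that a keratin rise with unchanged elasticity would be reported as improved fragility. The documents contain no success criterion or reporting rule that says so, and reading the two kinds of data jointly is an equally natural interpretation.

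The reply does not close the gap. No section says that the readings stand for fragility, neither objective includes them, and Section 9 treats elasticity as a question of its own. The narrower aims stated elsewhere show what the study can answer, but the primary objective still claims more.

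**Conclusion.** The point holds as a mismatch between objective and outcome. Fragility is undefined, the primary objective infers it from K16/K17 induction, and the only mechanical data are tied to no objective and no stated analysis. The plan permits an unsupported reading of a keratin result but does not prescribe one.

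The size is a matter of counting: none of the planned measurements is defined as fragility, and neither of the two objectives names either device. No bias or loss of power can be attached to it. The conclusion assumes that the open-ended laboratory work-up hides no fragility measure specified elsewhere. Whether elasticity is a valid proxy for fragility cannot be settled from these documents, and the conclusion does not rely on an answer. The keratin comparison is not called into question by this point.

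**What to change.** 1. Restrict the primary objective and its conclusion to K16/K17 induction. State that fragility is not directly assessed and that any link to it is a hypothesis.
2. Add elasticity as a secondary objective with one device parameter named in advance, for example the cutometer's measure of return to the original state, which Section 6 already describes.
3. In Section 7, specify the within-person sulforaphane-minus-vehicle difference and its test, only where a vehicle site exists: Group A photoexposed forearm after treatment, and Group B Test Area #1 versus #2 after UV.
4. For Group A's photoprotected site, report the before-after change only, and say that it cannot be separated from an effect of oil and occlusion.
5. Take Group A's Visit 2 readings away from the Visit 1 biopsy wounds, or record their proximity as a limitation.

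This changes wording and adds one analysis of readings already planned, with no new visits or procedures. The price is a narrower headline claim, and the elasticity result will be silent on a vehicle-controlled effect in Group A's photoprotected skin. If the investigators want to keep a fragility conclusion, they would need to define a fragility outcome in advance, or name elasticity as its proxy and justify that choice.

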While much is known regarding the dermal changes that occur with skin aging⁸, there has been little research in the role that keratins and epidermis play in skin aging and the associated skin fragility. It is also not know whether UV exposure has an effect on epidermal keratins. By assessing the epidermal structure of the skin from both photoprotected and photoexposed sites from individuals before and after the application of sulforaphanes, and before and after acute UV light exposure, we hope to understand whether differences exist in the expression of keratins between photoprotected and photoexposed areas and whether sulforaphane can change these differences.

4. Study Procedures

a) Study design, including the sequence and timing of study procedures

Recruitment: Individuals will be recruited from patient populations seen at the general dermatology clinics of Johns Hopkins Department of Dermatology or from patient populations participating in Johns Hopkins Cutaneous Translational Research Program (CTReP) research studies. Interested study participants will be evaluated after their routine clinical care visits. Participants will also be recruited from other patient populations in the Johns Hopkins Health System through the use of flyers. Study procedures will be conducted at the Johns Hopkins CTReP office located at the Johns Hopkins Outpatient Center. Recruitment may include Johns Hopkins University employees or students but these groups will not be specifically targeted for participation. Interested individuals will be interviewed to see whether they meet the basic eligibility criteria to participate in the study. Once eligibility has been demonstrated, the potential subjects will be instructed to make their first study appointment. We will recruit up to 50 participants over the age of 18 with healthy skin and they will be split into 2 groups: Group A) 20 volunteers that will apply sulforaphane in jojoba oil for up to 7 consecutive nights and have biopsies before and after on both photoprotected and photoexposed areas and jojoba oil only only to photoexposed areas for up to 7 consecutive nights with biopsy after 7 days Group B) 20 volunteers that will have 2 test areas irradiated with UV light and biopsies before and 24 hours after UV light irradiation; one of the UV treated areas will be pre-treated with sulforaphane for up to 7 consecutive nights and the other UV treated areas will be pre-treated with jojoba oil.

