Date: 06/16/2017 Principal Investigator: [name], MD Application Number: IRB00105668

Group A

Visit 1(day 0):

During the first scheduled appointment, the research protocol will be discussed with the subject and documentation will be obtained of the subject's consent to participate in the study and the subject's agreement to be contacted about future research studies. Photographs and clinical assessment will be taken.

Once informed consent is obtained, investigators will identify two suitable areas on the photoexposed forearm and one suitable area of the photoprotected upper inner arm for study. Each participant will receive up to 14ml of broccoli sprout extract (BSE) in jojoba oil, containing 7000nmol of sulforaphane. 500nmol of sulforaphane will be applied each night on each suitable

area for up to 7 consecutive nights. Additionally, each participant will receive up to 14 ml of jojoba oil only to be applied each night on one of the photoexposed site. All areas will be occluded with saran wrap every night. A demonstration and verbal instructions for how and where to apply study drug will be provided to subjects.

During this visit, investigators will perform clinical assessments, elasticity measurements, and up to two 6 mm punch, one from each area.

Visit 2 (up to day 7):

During this visit, investigators will perform clinical assessment, elasticity measurements and up to three 6 mm punch, one from each area.

Visit 3 (day 10-14): During this visit investigators will remove sutures from biopsies taken on visit 1.

Visit 4 (day 17-21):

During this visit investigators will remove sutures from biopsies taken on visit 2.

Group B

Visit 1:

During the first scheduled appointment, the research protocol will be discussed with the subject and documentation will be obtained of the subject's consent to participate in the study and the subject's agreement to be contacted about future research studies. Photographs and clinical assessment will be taken.

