Once informed consent is obtained, investigators will identify 2 suitable test areas on the photoprotected upper inner arm for study. Test area dimensions will be about 17 x 17 mm in diameter, the spot size produced by the department's UV device. Each participant will receive up to 7 ml of broccoli sprout extract (BSE) in jojoba oil, containing 3500nmol of sulforaphane and up to 7 ml of jojoba oil only 500 nmol of sulforaphane will be applied each night to Test Area #1 for up to 7 consecutive nights. Additionally, jojoba oil only will be applied each night to Test Area #2 for up to 7 consecutive nights. Areas will be occluded with saran wrap every night. A demonstration and verbal instructions for how and where to apply study drug will be provided to subjects. Clinical assessment and elasticity measurements will be performed during this visit as well.

Visit 2:

UV Light Irradiation: Within 1 to 7 days of BSE and jojoba oil only application, investigators will deliver a fixed dose of UV light to Test Area #1 and Test Area #2. Subjects will be asked to return on-site up to 3 days after UV exposure for biopsy.

Visit 3:

During this visit, investigators will perform clinical assessment, elasticity measurements and three 6 mm punch, one from each Test Area and one from normal, unirradiated skin, also on the upper inner arm, to serve as a control.

Visit 4:

Subjects will return on-site 10-14 days after biopsy to have sutures removed.

Photography: Standardized digital photographs will be obtained by study staff using a digital camera and software under standard photographic conditions at each study visit. Participants' eyes will be blacked out to de-identify facial photos. Photograph files will be coded to remove personal identifiers and stored on a secure hard drive in CTReP.

Clinical assessment: Clinical assessments will be performed to 1) record baseline skin findings 2) to identify up to 4 suitable areas for biopsy, 3) give information/demonstration about sulforaphane application and 4) to identify occurrence of any adverse events.

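### Group B biopsy is set at 24 hours after UV in the design summary but at any time up to 3 days in the visit schedule, and the nights of application before UV are not fixed

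*Combined protocol and SAP*

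**What the plan says.** The end of the Recruitment paragraph in section 4a summarises the design of each group. For Group B (20 volunteers) it specifies "biopsies before and 24 hours after UV light irradiation", and says that one irradiated area "will be pre-treated with sulforaphane for up to 7 consecutive nights" while the other is pre-treated with jojoba oil.

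The Group B visit schedule in the same section reads differently:

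- Visit 1: "500 nmol of sulforaphane will be applied each night to Test Area #1 for up to 7 consecutive nights". Jojoba oil alone goes on Test Area #2 under its own limit of up to 7 nights.
- Visit 2: "Within 1 to 7 days of BSE and jojoba oil only application, investigators will deliver a fixed dose of UV light" to both areas. Then: "Subjects will be asked to return on-site up to 3 days after UV exposure for biopsy".
- Visit 3: "three 6 mm punch, one from each Test Area and one from normal, unirradiated skin".

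None of the Group B visits carries a day number. In Group A the post-treatment biopsy visit is also open-ended ("Visit 2 (up to day 7"), and the Skin biopsies paragraph again describes treatment as lasting up to 7 days. A fixed length appears in only two places: the abstract, where participants "use topical sulforaphane for 7 days", and the design-summary phrase on the Group A jojoba-only biopsy, which is to follow 7 days.

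**The concern.** The secondary objective is the change in keratin expression after acute UV, alone and with sulforaphane, read from RNA and protein in the biopsies. Such a result describes a particular time after irradiation and a particular pre-treatment. If sites follow the visit schedule as written, biopsies at different times after UV, preceded by different numbers of applications, will be pooled across 20 volunteers. The estimate would then be an average over whatever mix of times and exposures occurred, and could not be reported as the 24-hour effect that the design summary describes.

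Nothing later in the document resolves this. Section 7 names the assays but gives no analysis, so no adjustment for timing or exposure is planned. The document does not ask for the number of applications, the hours since the last application or the hours since UV to be recorded. Section 10 ties payment to correct application of sulforaphane without saying how many nights that means.

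**Working it through.** **1. The plan's own supply figures.** Inputs: 500 nmol per site per night; 3500 nmol supplied in Group B (one sulforaphane site); 7000 nmol supplied in Group A (two sulforaphane sites). All are from section 4a, Visit 1 of each group.

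- Group B: 500 × 7 nights × 1 site = 3500 nmol, as stated.
- Group A: 500 × 7 nights × 2 sites = 7000 nmol, as stated.

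Both supplies equal exactly 7 nights.

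**2. Exposure the Group B text allows.** Taking 1 to 7 days as the length of application before UV:

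- 1 night: 1 × 500 = 500 nmol on Test Area #1
- 7 nights: 7 × 500 = 3500 nmol
- ratio 3500 / 500 = 7

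**3. Time from UV to biopsy.**

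| Place in section 4a | Time after UV | Is 24 h allowed? | Is 72 h allowed? |
|---|---|---|---|
| Design summary | 24 hours | yes | no |
| Group B, Visit 2 | up to 3 days (3 × 24 = 72 h) | yes | yes |

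The two agree only at 24 hours, and the document does not say which governs. The 3-week limit in section 4b does not settle it. With 7 nights (days 0 to 6), UV on day 7 and biopsy on day 10, sutures can come out from day 10 + 10 = 20, still within 21 days.

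**4. Group A.** Sutures from Visit 2 are removed at Visit 4, on days 17 to 21. The Skin biopsies paragraph asks for removal 10 to 14 days after biopsy. If Visit 2 falls on day d, Visit 4 is 17 − d to 21 − d days later.

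- d = 7 gives 10 to 14 days, so the whole window complies.
- The windows still overlap as long as 17 − d ≤ 14, that is d ≥ 3. At d = 3 the interval is 14 to 18 days.

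Keeping both suture rules therefore limits Group A to 3 to 7 nights, or 3 × 500 = 1500 to 3500 nmol per site. Only day 7 fits the whole window.

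**5. What the timing can and cannot distort.** Both test areas are irradiated at Visit 2, and all three Group B punches are taken at Visit 3. Within a participant, hours since UV are therefore the same on the sulforaphane and jojoba areas, and biopsy timing cancels as a source of bias in that contrast. It varies between participants.

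**6. Does a fixed schedule fit the other rules?** Visit 1 on day 0, applications on the nights of days 0 to 6, UV on day 7, biopsy on day 8. Suture removal runs from 8 + 10 = 18; 8 + 14 = 22 is cut to 21 by the 3-week limit. Days 18 to 21 are 10 to 13 days after biopsy. The supply, the 24-hour time, the suture interval and the 3-week limit are all met.

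**The case against.** The best case against is that 7 nights is plainly intended. The supply is exact, the abstract says 7 days, and the Group A suture visit falls precisely 10 to 14 days after day 7. On this view the open wording is a ceiling on exposure that leaves room for stopping early or rebooking, and a 7-fold spread in dose is a literal extreme. Much of that stands: a reader should not infer that 1-night courses are expected. But the Group B schedule permits them, and it is the operative text.

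A second objection is that the study is exploratory by its own description in section 8, sets no test or precision target, and offers no time course or variance, so no consequence can be demonstrated. The size is indeed unknown. A reader might want to convert the heterogeneity into lost precision or lost volunteers; the documents give nothing on which to base such a figure. The contradiction does not depend on one.

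A third is that 24 hours is not shown to be better than 48 or 72, and any single time would remove the conflict. That is correct. The reason to choose 24 hours is that the plan already states it.

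Finally, the Visit 2 wording could be read as a gap after the last application. Beside text describing pre-treatment over consecutive nights, that reading is strained, and the point does not rely on it.

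**Conclusion.** The point holds as an internal contradiction on biopsy time, together with a treatment length that the operative schedule leaves open. The text allows a Group B biopsy at up to 72 hours against a stated 24, and 500 to 3500 nmol on Test Area #1 before UV. The consequence is avoidable between-person heterogeneity of unknown size and a UV effect not tied to the stated time point. It should be corrected but does not invalidate the design.

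Two stronger inferences are not supported. One is that biopsy timing biases the sulforaphane versus jojoba comparison; the single biopsy visit rules that out. That reassurance covers timing only. Equal numbers of applications on the two areas are a natural inference but are not required by the text. The unirradiated control site is not assigned oil or occlusion, which is a separate matter. The other is that the plan names no time point at all: it names 24 hours, and the visit schedule then departs from it.

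The dose range assumes at least one night of application and reads 1 to 7 days as the length of treatment.

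**What to change.** In the Group B schedule of section 4a, replace the open wording with a dated sequence:

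- Visit 1 on day 0, with 7 nightly applications on both test areas;
- UV on day 7, the day after the seventh night;
- biopsy 24 hours after UV (day 8), with a narrow stated window;
- suture removal on days 18 to 21.

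Set Group A Visit 2 to day 7.

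Allow early stopping for irritation, which section 8 lists as a risk. Stop both Group B areas together so that they stay matched, and let the investigator decide whether UV and biopsy go ahead; if they do, keep the 24-hour rule. Record the number of applications, the hours since the last application and the hours since UV. Keep every biopsied participant in whatever analysis is adopted, and use the recorded timings only in a sensitivity analysis.

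The cost is protocol wording, three fields on the visit form and less scheduling freedom. Assuming a Monday-to-Friday clinic, Group B could not start on a Friday, because the day-8 biopsy would fall on a Saturday.
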